### 13.2.3 Dynamic mechanical allodynia

For a detailed description of the dynamic mechanical allodynia assessment please see protocol Section 12.3.2. Allodynia is rated on an 11-point NRS and assessed 5 times. A value of “10” corresponds to the individual maximum pain imaginable. The degree of pain sensitivity is calculated by the geometrical mean of the five pain ratings given (Maier et al. 2010).

The change from baseline in the DMA will be analyzed using a similar model as for average pain intensity. Only subjects with allodynia at baseline, i.e., a DMA score greater than 0 on the 0 to 10 NRS, will be included in the analysis.

In addition, descriptive summaries will be generated for the degree of pain sensitivity and displayed together with the respective changes from baseline.

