12.3.2 Dynamic mechanical allodynia

Allodynia is defined as pain in response to a non-nociceptive stimulus. In cases of mechanical allodynia, even gentle mechanical stimuli such as a slight bending of hairs can evoke pain. The DMA is assessed by the investigator, documented in the source data, and transferred to the eCRF. A Q-tip fixed to an elastic strip exerting a force of 100 mN (Ziegler et al. 1999) is applied in a single sweeping motion (1 cm to 2 cm length) on the skin of the affected limb.

The subjects are asked to judge the stimulus intensity on an NRS (0 to 10), with “0” in this case meaning “no pain”, while each “pricking”, “stinging” or “burning” sensation is defined as a painful sensation, being evaluated by giving a value greater than “0”. A value of “10” corresponds to the individual maximum pain imaginable. The tactile stimulus is tested 5 times. If the subject reports a value of “10”, then no further test will be performed for the respective visit. The degree of pain sensitivity is calculated by the geometrical mean of the pain ratings given (Maier et al. 2010).

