14.1.7.2 Analysis of the secondary efficacy endpoints

All secondary efficacy endpoints will be analyzed for the Full Analysis Set.

Average pain intensity

The change from baseline in the average pain intensity, recorded on the tablet computer, will be analyzed with an MMRM, including the covariate baseline pain intensity score, and the factors geographic region, week, treatment, and treatment-by-week interaction as fixed effects, and subject as random effect. An unstructured covariance matrix will be used to model the covariance structure.

The analysis will be performed using the contrast, i.e., the mixed model Wald test, of 400 mg neridronic acid versus placebo at Week 26 of the treatment, week and treatment-by-week interaction term of the mixed effects model described above. Model-based parameter estimates, standard errors, 95% confidence intervals, and p-values will be tabulated. This analysis will be performed using the observed values without imputation of missing values.

Pain response to treatment

Pain response to treatment, defined as an at least 30% decrease from baseline in average pain intensity, recorded on the tablet computer, will be derived. If a subject shows a worsening or the pain intensity score for the respective visit is missing then the subject will be considered a pain non-responder for the respective visit. A logistic regression model at Week 12 and Week 26 will be fitted to the data, including the covariate baseline pain intensity score, and the factors geographic region, and treatment as fixed effects. Model-based parameter estimates, standard errors, 95% confidence intervals, and p-values for the odds ratio at Week 12 and Week 26 between 400 mg neridronic acid and placebo will be tabulated.

The analysis of pain response to treatment will include a cumulative responder analysis at Week 12, Week 26, and Week 52, where responder rates will be calculated for different percentage thresholds for decrease from baseline in average pain intensity.

Dynamic mechanical allodynia

The change from baseline in the DMA will be analyzed using a similar model as for average pain intensity. Only subjects with allodynia at baseline, i.e., a DMA score greater than 0 on the 0 to 10 NRS, will be included in the analysis.

Pressure pain threshold

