To assess the efficacy of a cumulative dose of 400 mg intravenous neridronic acid versus placebo on the dynamic mechanical allodynia (DMA).	Change from baseline to Week 12 in the pain intensity level of DMA.	
Dynamic mechanical allodynia: a tactile stimulus is applied in a single sweeping motion (1 cm to 2 cm length) on the skin on the affected limb.
 
The subjects are asked to judge the stimulus intensity by means of an NRS (0 to 10). “0” in this case means “no pain”. Each “pricking”, “stinging” or “burning” sensation is defined as a painful sensation, which should always be evaluated by giving a value greater than “0”. “10” corresponds to the individual maximum pain imaginable.
 
The change from baseline (Visit 2 [Day 1]) to Visit 8 (Week 12) will be analyzed.

To assess the efficacy of a cumulative dose of 400 mg intravenous neridronic acid versus placebo on the pressure pain threshold (PPT).	Change from baseline to Week 12 in the PPT ratio for the thenar muscle/abductor hallucis muscle.	
Pressure pain threshold: using a pressure algometer (contact area 1 cm^2), the threshold for pressure-induced pain is measured on the thenar muscle/abductor hallucis muscle in 3 series of slowly increasing stimulus intensities (at a rate of about 50 kPa/s). The threshold is then determined as the arithmetic mean of the 3 series (in kPa).
 
The ratio of the thresholds of the affected limb versus the unaffected limb will be calculated.
 
The change from baseline (Visit 2 [Day 1]) to Visit 8 (Week 12) will be analyzed.

To assess the efficacy of a cumulative dose of 400 mg intravenous neridronic acid versus placebo on edema of the hand or foot.	Change from baseline to Week 12 in the ratio of the figure of eight measurements of the affected limb versus the unaffected limb.	
In subjects with the CRPS sign of edema on the CRPS Severity Score at baseline, circumference of the hand or foot will be measured by the investigator with measurement tape using the figure-of-eight method at both the affected limb and the contralateral unaffected limb. Each measurement will be performed 3 times. The average of the 3 measurements will be used for further analysis.
 
The ratio of the averages of the affected limb versus the unaffected limb will be calculated.
 
The change from baseline (Visit 2 [Day 1]) to Visit 8 (Week 12) will be analyzed.

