### **13.2.6 Confirmatory testing strategy for secondary endpoints**

A confirmatory testing procedure will be used for testing of the superiority of neridronic acid 400 mg versus placebo with respect to the primary and selected secondary efficacy endpoints (change from baseline to Week 26 in the average pain intensity, change from baseline to Week 12 in the pain intensity level of DMA, change from baseline to Week 12 in the PPT ratio, and change from baseline to Week 12 in the ratio of figure of eight measurements).

First, the primary endpoint will be tested at a one-sided level  $\alpha = 2.5\%$ . If the first test is statistically significant, the 4 secondary endpoints will be tested in a second stage.

To control for the family-wise type I error rate at the one-sided 2.5% level, a hybrid Hochberg-Hommel step-up procedure (hybrid-0 procedure in Gou et al. 2014) will be applied. The testing procedure uses the ordered p-values  $p_{(1)} \geq p_{(2)} \geq p_{(3)} \geq p_{(4)}$ . At first, if the largest p-value  $p_{(1)} \leq \alpha$ , then all 4 hypotheses are rejected. Otherwise the associated null hypothesis  $H_{(1)}$  is accepted and testing proceeds to the next step. In general, at Step  $i = 2, \dots, 4$ , if  $p_{(i)} \leq c_i \alpha$ , then any hypothesis with p-value  $\leq d_i \alpha$  will be rejected and testing stops; otherwise, the null hypothesis  $H_{(i)}$  is accepted and testing continues at the next step. At Step 4, the null hypothesis  $H_{(4)}$  is rejected if  $p_{(4)} \leq \alpha/4$ ; otherwise  $H_{(4)}$  is accepted. The constants used in the testing procedure are defined by  $c_i = (i+1)/(2i)$  and  $d_i = 1/i$  and are given in the table below.

I	1	2	3	4
$c_i$	1	3/4	2/3	5/8
$d_i$	1	1/2	1/3	1/4

This semiparametric multiple testing procedure controls the family-wise error rate in the strong sense if the test statistics follow a multivariate normal distribution with non-negative correlation coefficients (Gou et al. 2014) which can be assumed for the investigated 4 efficacy endpoints.

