**19.1.4 Efficacy analysis**

Not applicable.

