#### **Derivation of geometric mean and geometric coefficient of variation**

Geometric mean =  $\exp(\text{arithmetic mean of log-transformed values})$

Zeros will be excluded from the calculation of the geometric mean.

Geometric. CV% =  $(\text{sqrt}(\exp(\text{variance for log transformed data}) - 1)) * 100$

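### DMA at Week 12, an alpha-controlled secondary endpoint, is scored as a plain geometric mean of 0-10 ratings, so any single 0 sets the whole visit to 0

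*SAP*

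**What the plan says.** Each stroke is rated on an 11-point scale on which 0 means no pain, and five strokes are applied per visit. The two documents score them in nearly the same words.

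- SAP 13.2.3: "The degree of pain sensitivity is calculated by the geometrical mean of the five pain ratings given".
- Protocol 12.3.2: "The degree of pain sensitivity is calculated by the geometrical mean of the pain ratings given".

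Both attach a literature citation to that sentence. Neither gives a zero rule, an offset or a transformation.

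The analysis is restricted to subjects with allodynia at baseline, defined in SAP 13.2.3 as "a DMA score greater than 0 on the 0 to 10 NRS". Protocol 1.5.3.2 and 14.1.7.2 use the same filter.

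The endpoint "change from baseline to Week 12 in the pain intensity level of DMA" is one of the four secondary endpoints tested in SAP 13.2.6 after the primary, by a step-up procedure at one-sided 2.5%.

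In the SAP's derivation appendix, section 19.1.4 (efficacy) is marked as not applicable. The one zero rule, "Zeros will be excluded from the calculation of the geometric mean", stands under 19.1.5 on pharmacokinetic and pharmacodynamic parameters. It is called from SAP 14.1 for plasma concentrations.

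**The concern.** A geometric mean is a root of a product, so one zero factor makes it zero whatever the other ratings are. Zero is an ordinary answer on this scale. The stated rule therefore cannot separate a visit with some painful strokes from one with none, and that happens near the floor, where responders are expected to move.

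The same property reaches the analysis set. If the filter is applied to the computed score, one painless baseline stroke removes a subject who reported pain on the other four, although the stated purpose is to keep subjects with allodynia.

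This is a confirmatory test, so its score and its subset should each have one possible derivation. A noisier DMA p-value also matters beyond DMA: at the first step all four hypotheses are rejected only if the largest p-value is at most 0.025.

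**Working it through.** **1. The plan's own sample-size figure.** The documents give no SD, effect or sample size for DMA. The only related figure is for the primary endpoint: difference 1.0, SD 2.0, one-sided 0.025, 90% power, 86 per arm. A two-sample t-test needs 85.03, which rounds up to 86. The figure reproduces and is not in dispute.

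**2. The scoring arithmetic (no assumptions).** Plain score = (product of ratings)^(1/5). With a constant c: (product of (rating + c))^(1/5) - c.

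| Ratings | Plain | Zeros excluded | c = 0.1 | c = 1 | Arithmetic |
|---|---|---|---|---|---|
| 2,2,1,1,1 | 4^(1/5) = 1.32 | 1.32 | 1.32 | 1.35 | 1.40 |
| 2,2,1,1,0 | 0 | 4^(1/4) = 1.41 | 0.78 | 36^(1/5) - 1 = 1.05 | 1.20 |
| 0,0,0,0,6 | 0 | 6.00 | 0.13 | 0.48 | 1.20 |
| 0,0,0,0,0 | 0 | undefined | 0 | 0 | 0 |

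Changing one rating from 1 to 0 drops the plain score from 1.32 to 0, level with five painless strokes. Borrowing the pharmacokinetic rule does not help. The same change would raise the score from 1.32 to 1.41, one painful stroke in five would score 6, and a painless visit would have no score.

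**3. Illustration of the loss (all inputs assumed).** Latent baseline rating N(4, 2.5); stroke-to-stroke SD 0.5, 1.0 or 1.5; latent change -1 on placebo and -2 on active, change SD 2. Ratings are rounded and clipped to 0-10, and testing stops after a 10 as in protocol 12.3.2. Effects are standardised by the residual SD after baseline adjustment. Factor in subjects = (effect of rating + 1 score / effect of plain score)^2, taken before rounding, so the last digit can differ slightly from the effects shown.

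| Stroke SD | 0.5 | 1.0 | 1.5 |
|---|---|---|---|
| Share of subjects with any painful baseline stroke kept by plain score > 0 | 0.926 | 0.848 | 0.763 |
| Filtered subset: plain / rating + 1 effect | 0.464 / 0.470 | 0.441 / 0.455 | 0.406 / 0.429 |
| Factor, same filtered subjects | 1.03 | 1.07 | 1.11 |
| Any painful baseline stroke: plain / rating + 1 effect | 0.448 / 0.459 | 0.413 / 0.438 | 0.370 / 0.409 |
| Factor, same unfiltered subjects | 1.05 | 1.13 | 1.22 |
| Plain on filtered subset against rating + 1 on all, divided by share kept | 1.06 | 1.17 | 1.34 |

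The last row mixes two things. Dividing it by the same-subset factor leaves about 1.03, 1.09 and 1.21 for the change of population.

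The excluded subjects sit near the floor: mean arithmetic score 0.6 / 1.0 / 1.5, with under 1% at 4 or more. Without the filter on the score, 11% / 21% / 31% of placebo and 13% / 26% / 37% of active subjects have mixed ratings at Week 12 and score 0. Their mean arithmetic score is 0.6 to 1.2.

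For latent means from 3 to 6, exclusion runs from 2% to 35%. The unfiltered same-subject factor runs from 1.02 to 1.30, and the mixed factor from 1.02 to 1.54.

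**The case against.** **The size rests on no trial data.** This stands. Mean, spread, stroke variability and effect are all assumed. The arithmetic in step 2 does not depend on them.

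**The cited scoring source may contain a zero rule.** That cannot be checked here, and it should be checked first. The SAP nevertheless writes the formula out itself with no such rule, and a programmer following the text would obtain 0.

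**The filter is clear enough.** Largely so. The wording is singular, one derived value per visit enters the model, and a geometric mean of 0-10 ratings lies on that range. A reader might infer that the subset is wholly undetermined, but the documents lean towards the computed score. Some doubt remains because that score goes by another name (degree of pain sensitivity) and the scale named is that of a single rating. The natural reading is also the one that excludes subjects with mixed ratings.

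**Restricting to subjects with allodynia is deliberate, so dropping near-floor subjects is not lost efficiency.** This stands in part. It is why the 1.06 to 1.34 row should not be credited to the score alone.

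**The SAP's five ratings conflict with the stop at 10.** A reader might call this an error. The SAP is written to the protocol dated 14 March 2018, and the stop came with Amendment 01, so only alignment is needed.

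**Conclusion.** The defect holds on the text. As written, the confirmatory DMA score is 0 whenever one rating is 0, and no rule for DMA prevents it. On the natural reading of the filter, subjects with allodynia and one painless baseline stroke are also excluded. It should be fixed, as a secondary-endpoint matter.

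The illustrative cost of the score alone is a factor of 1.03 to 1.11 in subjects on the filtered subset, or 1.05 to 1.22 on all subjects with any painful baseline stroke, at a latent mean of 4 and the other inputs listed.

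Three stronger conclusions are tempting and are not supported:

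- **False positives or bias towards the drug.** The rule is applied identically in both arms, so no type I error inflation is claimed, and the documents establish no fixed direction of bias.
- **Subjects with marked allodynia routinely scored as painless.** A set such as 8, 8, 8, 8, 0 does score 0, but in the model such subjects are rare and those affected are near the floor.
- **A count of trial subjects lost.** This would need a DMA rating distribution, which the documents do not give.

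**What to change.** Before unblinding:

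1. In SAP 13.2.3 and protocol 12.3.2, state one zero-tolerant score for every visit, computed over the ratings obtained. Use the cited source's zero rule if it has one. Otherwise use a geometric mean with a stated constant added to every rating and then subtracted (for example rating + 1, minus 1), or the arithmetic mean. Do not borrow the pharmacokinetic rule of excluding zeros.
2. In SAP 13.2.3 and protocol 1.5.3.2 and 14.1.7.2, define the subset as subjects with any Visit 2 rating above 0.
3. Keep the plain geometric mean as a sensitivity analysis.

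The ratings are already collected. The cost is a small, documented change to the scoring of a pre-specified secondary endpoint, with edits to the SAP and three protocol sections. The constant is a convention: a smaller one stays closer to the plain geometric mean (0.78 with 0.1 against 1.05 with 1 for 2, 2, 1, 1, 0). What matters is that it is fixed in advance.

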### 13.2.4 Pressure pain threshold

For a detailed description of the pressure pain threshold please see protocol Section 12.3.2. Pressure pain threshold will be measured at both the affected and unaffected limb for all subjects. Measurements are repeated in 3 series of slowly increasing stimulus intensities and the respective

pressure pain threshold is documented. For the final PPT, the arithmetic mean of all 3 consecutive measurements is calculated (Rolke et al. 2010, Mainka et al. 2014).

The ratio of the thresholds of the affected and the unaffected (denominator) limb will be calculated.

The change from baseline in the ratio of the PPT in the affected limb to the PPT in the unaffected limb for the thenar muscle/abductor hallucis muscle will be analyzed using a similar model as for average pain intensity. Only subjects with deep somatic pain (PPT  $\leq 300$  kPa) in the affected limb at baseline will be included in the analysis.

In addition, descriptive summaries will be generated for the ratio of the thresholds as well as for the changes from baseline.

### **13.2.5 Edema**

For a detailed description of the Edema measurement, please see protocol Section 12.3.4. Edema will be measured at both the affected and unaffected limb for all subjects having edema as a positive CRPS sign at baseline (based on clinical judgment; sign “Asymmetric edema” ticked “yes” on the CRPS Severity Score at Visit 2). Each measurement of the limbs will be performed 3 times. The average of the 3 measurements will be used for further analysis.

The ratio of the averages of the affected and the unaffected (denominator) limb will be calculated.

The change from baseline in edema will be analyzed using a similar model as for average pain intensity. Only subjects with presence of the CRPS sign “asymmetric edema” at baseline will be included in the analysis.

In addition, descriptive summaries including changes from baseline will be generated for the averages of the affected and the unaffected limb and the ratio of the two averages.

### **13.2.6 Confirmatory testing strategy for secondary endpoints**

A confirmatory testing procedure will be used for testing of the superiority of neridronic acid 400 mg versus placebo with respect to the primary and selected secondary efficacy endpoints (change from baseline to Week 26 in the average pain intensity, change from baseline to Week 12 in the pain intensity level of DMA, change from baseline to Week 12 in the PPT ratio, and change from baseline to Week 12 in the ratio of figure of eight measurements).

First, the primary endpoint will be tested at a one-sided level  $\alpha = 2.5\%$ . If the first test is statistically significant, the 4 secondary endpoints will be tested in a second stage.

To control for the family-wise type I error rate at the one-sided 2.5% level, a hybrid Hochberg-Hommel step-up procedure (hybrid-0 procedure in Gou et al. 2014) will be applied. The testing procedure uses the ordered p-values  $p_{(1)} \geq p_{(2)} \geq p_{(3)} \geq p_{(4)}$ . At first, if the largest p-value  $p_{(1)} \leq \alpha$ , then all 4 hypotheses are rejected. Otherwise the associated null hypothesis  $H_{(1)}$  is accepted and testing proceeds to the next step. In general, at Step  $i = 2, \dots, 4$ , if  $p_{(i)} \leq c_i \alpha$ , then any hypothesis with p-value  $\leq d_i \alpha$  will be rejected and testing stops; otherwise, the null hypothesis  $H_{(i)}$  is accepted and testing continues at the next step. At Step 4, the null hypothesis  $H_{(4)}$  is rejected if  $p_{(4)} \leq \alpha/4$ ; otherwise  $H_{(4)}$  is accepted. The constants used in the testing procedure are defined by  $c_i = (i+1)/(2i)$  and  $d_i = 1/i$  and are given in the table below.

I	1	2	3	4
$c_i$	1	3/4	2/3	5/8
$d_i$	1	1/2	1/3	1/4

This semiparametric multiple testing procedure controls the family-wise error rate in the strong sense if the test statistics follow a multivariate normal distribution with non-negative correlation coefficients (Gou et al. 2014) which can be assumed for the investigated 4 efficacy endpoints.

### 13.3 Other efficacy data

To assess the efficacy of neridronic acid in subjects with CRPS other data is collected as described in Section 1.2 of the protocol and will be analyzed as described in the following chapters. Descriptive summaries will be generated for all visits where data is assessed as per schedule of events in Section 1.7 of the protocol. Analysis will be presented per visit and treatment if not specified differently.

#### 13.3.1 Pain Intensity recording on the tablet computer.

Analysis will be performed by descriptively summarizing average, worst and current pain intensity recorded on the tablet computer by visit and treatment group. In addition, changes from baseline and changes from Week 26 will be displayed. The value at Visit 2 is considered as baseline value.

Graphical display of the worst and current pain recording by visit and treatment will be done in addition to the primary endpoint graphical display of the average pain intensity recordings.

In addition, analysis will be repeated for subgroups defined by subjects who are treated in Treatment Period B in combination with the responder definition based on duration of response as defined in Section 13.3.2.

#### 13.3.2 Pain response based on pain intensity recordings on the tablet computer

Pain response to treatment based on pain intensity recordings on the tablet computer will be analyzed based on the comparison timepoint, either baseline or Week 26.

##### Pain response as % decrease from baseline

Analyses are covered as part of secondary endpoint “Pain response to treatment” (see Section 13.2.2). In addition to the 30% responders and 30% non-responders a display with regards to the percentage threshold of 50% will be done. A 50% responder is a subject showing at least 50% pain decrease and a 50% non-responder being a subject with a missing pain intensity or a subject having less than 50% pain decrease.

##### Pain response as % decrease from Week 26

Descriptive statistics will be displayed for % decrease from Week 26 analogously to analysis of pain response as % decrease from baseline. This will be done using the pain intensity at Week 26 instead of baseline pain intensity for determination of the % decrease.

##### Duration of effect – Response based on duration of effect

The duration of effect for treatment period A is defined as the time from baseline to first loss of response. Response is defined as at least 30% decrease from baseline and first loss of response is

the first time after achieving response that a subject shows less than 10% decrease from baseline. Duration of effect is then the time from baseline till the last timepoint before first loss of response. Pain assessments (tablet computer) that are considered for this analysis are those at Day 1 (Baseline), Week 6, Week 12, Week 16, Week 22 and Week 26.

Subjects never reaching a 30% decrease from baseline will have a duration of effect of 0 weeks. Subjects reaching a 30% decrease from baseline but showing no loss of effect, i.e. not dropping to below 10% decrease from baseline afterwards, will be censored at Week 26 with a duration of effect of 26 weeks. Else the duration of effect is taken as the last assessment a subject shows an effect (at least 30% response) before first experiencing a loss of response. e.g., if subject shows less than 30% decrease at Week 6, at least 30% decrease at Weeks 12 and 16 and at Week 22 less than 10% decrease, the duration of effect is set to 16 weeks.

Duration of effect will be analyzed using survival analyses with timepoints respective to the visits where pain is assessed on the tablet computer. A frequency table for the duration of effect will be provided for Follow-Up Period 1.

Furthermore, to assess the effect of a second treatment cycle, for those subjects who received two treatment cycles of neridronic acid, descriptive statistics for the change in average pain intensity from baseline, the change in average pain intensity from Week 26 and pain response as % decrease from baseline and from week 26 will be displayed for Follow-up Period 2 for the following responder subgroups based on duration of effect.

- Never-responders: subjects with a duration of effect = 0 weeks.
- Lost-responders: Subjects with a duration of effect <26 weeks.
- Responders: subjects with a duration of effect =26 weeks.

